6.5 SAMPLE SIZE

Currently, there are approximately 4000 eligible patient-encounters over a six-month period at our study practices. Given prior work showing the algorithm flags 8-10% of eligible patients as high-risk, we anticipate enrolling at least 360 patients. The unit of analysis is the patient. We will use multilevel mixed-effects models, adjusted for relevant covariates, to assess outcomes. Assuming baseline palliative care rate=26.9% (SD=10%), a 10% dropout rate, two-sided alpha=0.05, a sample of 360 patients (180 intervention, 180 control) will provide 80% power to detect a meaningful 15 percentage-point increase in palliative care visits.

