4. STUDY DESIGN

4.1 RANDOMIZATION & RECRUITMENT

This 2-arm randomized trial (six-month enrollment; six-month follow-up) will enroll approximately 400 patients with advanced lung and gastrointestinal malignancies and 40 clinicians to assess response to behavioral nudges to refer to palliative care at up to 17 practices within Tennessee Oncology, a US community oncology network. All practices have access to palliative care and will be randomized to usual care vs. intervention. The outcome is completion of a palliative care visit within 3 months among high-risk patients.

We will randomize practices into two arms using permuted block randomization to balance practice size, baseline palliative care referral rate (see **Exhibit 1**). The Principal Investigator ([name]) and primary statistical analyst will be blinded to arm assignment.

This 2-arm randomized trial (six-month enrollment, six-month follow-up) is taking place at Tennessee Oncology. Tennessee Oncology, one of the nation’s largest, community-based cancer care specialists, is home to one of the leading clinical trial networks in the country.

Eligible clinicians will receive notification about the trial via email and in-person presentations. High-risk patients for the intervention will be identified from weekly runs of the risk score algorithm, in coordination with [name], Tennessee Oncology Care Data Systems Manager.

For the semi-structured interviews, the research team at Tennessee Oncology will create a list of potential clinicians. We will initially contact potential participants via email (see **Exhibit 6**), and if we do not get enough participation, coordinator and site investigator will do in-person recruitment with clinicians. For participants that agree to do the interview, clinical research coordinator will create a research ID for each participant that only key members of research team will have access to. Coordinator will subsequently create a de-identified dashboard to track mode of interview (in-person, virtual, telephone), length of interview, participant characteristics (gender, years in practice, palliative care v oncology, physician v nurse practitioner), and to store audio files, transcripts, and analysis documents. To ensure an adequate number of perspectives on the trial, we will use purposive

sampling to sample clinicians who performed at or above vs. below the median response to the intervention.

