4.4 TARGET POPULATION

Approximately 400 patients with advanced malignancies and up to 80 clinicians to assess response to behavioral nudges to refer to palliative care at up to 17 practices within Tennessee Oncology. The split will be into two arms: approximately 200 intervention, 200 control, and up to 40 clinicians in each arm. Clinicians will be clustered to a single practice for the intervention and analysis in order to avoid contamination of intervention effect into the usual care arm.

Our target population for the semi-structured interviews includes clinicians at Tennessee Oncology that were included either in the intervention group as oncology providers, and palliative care clinicians at Tennessee Oncology that saw patients referred through our intervention.

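### Section 6.5 names no few-cluster inference method for at most 17 randomised practices; a default normal-reference test would have a type I error of roughly 5–9%

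*Combined protocol and SAP*

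**What the plan says.** Section 4.1 makes the practice the unit of randomisation ("We will randomize practices into two arms using permuted block randomization to balance practice size, baseline palliative care referral rate") and caps the number of practices ("at up to 17 practices within Tennessee Oncology"). Section 4.4 ties each clinician to one practice: "Clinicians will be clustered to a single practice for the intervention and analysis". Section 6.5 then states "The unit of analysis is the patient" and gives the whole inferential plan in one sentence: "We will use multilevel mixed-effects models, adjusted for relevant covariates, to assess outcomes". The nominal level is "two-sided alpha=0.05".

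The documents name no link function, random-effect level, estimator, test, degrees-of-freedom method, permutation test or ICC. Section 6.4 adds only the endpoint definitions and descriptive statistics for the exploratory outcomes. Nothing rules a small-sample method out.

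**The concern.** Treatment differs only between practices, about 8 against 9 at most. The precision of the treatment effect therefore depends on a between-practice variance estimated from very few units. A Wald z-test, a common software default for a binary mixed model, treats that variance as known, and maximum likelihood (ML) also tends to estimate it too low. Both push the p-value down and narrow the confidence interval.

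Two things are at stake. A false claim that default referral raises palliative care visits may be more likely than 5%, with an interval that under-covers. Also, Wald z, likelihood-ratio, REML and t-based tests give different p-values on the same data, so a borderline primary result could turn on a choice made after the data are seen.

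**Working it through.** **Inputs from the documents.** At most 17 practices (4.1, 4.4). From 6.5: 360 patients, 1:1; 10% dropout; control rate 26.9%; SD 10%, level not stated; effect +15 points; two-sided alpha 0.05.

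**Assumed, because the documents give none.** ICC, variation in practice size, estimator and test.

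**1. The plan's own figure.** Dropout leaves 360 × 0.9 = 324 patients, 162 per arm. For 26.9% against 41.9% the mean rate is 34.4%. The null SE is √(2 × 0.344 × 0.656 / 162) = 0.0528, and the SE under the alternative is √((0.269 × 0.731 + 0.419 × 0.581) / 162) = 0.0521. Power is Φ((0.15 − 1.96 × 0.0528) / 0.0521) = 81%, against the stated 80%. The figure reproduces only as an individually randomised comparison, so nothing in it shows that few-cluster inference was considered.

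**2. Analytic size of a z-test.** Between-practice df = 17 − 2 = 15.
- z reference where t(15) applies: P(|t15| > 1.96) = 6.9%.
- With ML variance shrinkage as well: P(|t15| > 1.96 × √(15/17)) = P(|t15| > 1.84) = 8.5%.
- If the two balancing variables in 4.1 were also in the model, 13 df would remain: P(|t13| > 1.96) = 7.2%. The plan does not name its covariates, so this is an illustration.

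**3. ICC implied by the stated SD.** If 10% is the SD between practices, ICC = 0.10² / (0.269 × 0.731) = 0.01 / 0.1966 = 0.051. An SD of 5 points would give 0.0025 / 0.1966 = 0.013.

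**4. Simulation under the null.** 17 practices, 324 or 360 patients, rate 26.9%, equal practice sizes or a size coefficient of variation (CV) of 0.6, no covariates, unrestricted randomisation, 4,000–8,000 replicates per setting (Monte Carlo SE about 0.3–0.4 points). Rejection rates in %:

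| ICC | Logistic ML, Wald z | Logistic likelihood ratio | Linear ML, z | Linear REML, z | Logistic ML, t(15) | Linear REML, t(15) |
|---|---|---|---|---|---|---|
| 0 | 4.2–4.7 | 3.9–4.4 | 4.5–4.9 | 4.0–4.4 | 2.7–3.2 | 2.4–3.0 |
| 0.01 | 5.6–6.0 | 5.2–5.3 | 5.7–6.5 | 5.1–5.5 | 3.9–4.1 | 3.5–3.8 |
| 0.02 | 6.4–7.0 | 5.7–5.9 | 6.7–7.3 | 5.6–6.0 | 4.6–4.7 | 4.1 |
| 0.03 | 7.1–8.0 | 6.1–6.9 | 7.3–8.5 | 6.1–7.0 | 4.9–5.6 | 4.1–4.7 |
| 0.051 | 7.7–8.1 | 6.6–7.0 | 8.1–8.6 | 6.5–6.9 | 5.6–6.2 | 4.8–5.3 |
| 0.10 | 7.7–8.7 | 6.8–7.0 | 8.2–9.1 | 6.7–7.2 | 5.8–6.5 | 4.8–5.3 |

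At ICC 0.02 and 0.03 only one sample size was run (324 and 360). At 0.051 and 0.10 the unequal-size runs use 360 patients only. Runs at ICC 0.20 are left out because the logistic fits there were numerically doubtful.

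Separate simulations with 340 patients and a between-practice SD of 10 points gave 8.1–8.9% for logistic ML Wald z (size CV 0.4–0.7). With an SD of 5 points they gave 5.5–6.5%.

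**5. Effect of the balanced randomisation.** Under the same 340-patient set-up (SD 10 points, size CV 0.5, 2,000 replicates), practices were randomised in blocks of 4 ordered on a baseline rate correlated 0.5–0.85 with practice propensity. Block size and correlation are assumptions. Logistic ML Wald z then rejected 4.6–6.7% unadjusted and 7.2–7.8% adjusted for that rate.

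**6. Power given up by using t(15).** The critical value rises from 1.960 to 2.131. With 324 patients and equal practice sizes, the design effect is 1 + (324/17 − 1) × ICC.

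| ICC | Design effect | Power, z | Power, t(15) |
|---|---|---|---|
| 0.01 | 1.18 | 75% | 70% |
| 0.03 | 1.54 | 64% | 58% |
| 0.051 | 1.92 | 55% | 49% |

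**The case against.** A reader might infer that the plan has no small-sample correction and a true type I error of about 8–9%. The documents support neither statement. Section 6.5 leaves the test open; Kenward–Roger, Satterthwaite, between-within df or permutation inference would all comply with it. The 8–9% figure needs ML estimation, a normal-reference test, an ICC of about 0.05 or more, and no allowance for the balancing in 4.1. The ICC rests on reading "Assuming baseline palliative care rate=26.9% (SD=10" per cent as a between-practice SD, which section 6.5 does not say. Nor do the documents support a worse figure from fewer practices: a run with 12 gave about 10% for logistic Wald z, but the only count stated is the ceiling of 17.

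It can also be said that the t reference is imperfect: with logistic ML it still runs near 6% at ICC 0.05, and it is conservative at very small ICC. And the missing allowance for clustering in the power statement is a larger, separate problem.

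These objections stand, and they cut the claim to a range. They do not remove it. Without balancing, every uncorrected method tested exceeded 5% once the ICC was appreciable, and modelling the balancing left 7.2–7.8% in the adjusted analysis, the form that 6.5 announces.

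**Conclusion.** The point holds as a gap in pre-specification with a measurable consequence. If a software default with a normal reference is used, the nominal 5% test has a true level of roughly 5–9% with 17 practices, or about 1.0 to 1.8 times the stated error. The lower end applies if the ICC is near zero or the balancing removes most between-practice variation. The upper end applies with ML, a z reference and an ICC of 0.05 or more. The range comes mainly from models without practice-level covariates; each one included would use a further degree of freedom.

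Confidence is high that the method is unspecified, and lower for any single figure in the range. This is an inexpensive improvement that should be made, not a flaw that by itself invalidates the trial.

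**What to change.** State in section 6.5 that the primary model includes a practice-level random effect, and name the link, the estimator and the covariates. Then specify one of the following for the primary p-value and confidence interval:

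- **Preferred:** a permutation test that re-randomises practices under the actual permuted-block scheme, with the interval obtained by inverting the test. The block structure must be recorded so that only admissible allocations are used.
- **Alternative:** a t reference for the mixed-model treatment effect with df equal to practices minus 2 minus the number of practice-level covariates, confirmed by that permutation test. The confirmation matters because logistic ML with t(15) can still run near 6%.

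The cost is a sentence in the SAP and modest programming. The interval becomes slightly wider and power falls by about 5 to 6 points in the calculation above (64% to 57% in a simulation with 340 patients and SD 10 points, where the higher figure comes from a test that does not hold 5%). If the ICC is very small, the t reference is conservative, at about 3.5–4% for ICC 0.01.

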4.9 ACCRUAL

Patients will accrue to the trial as their clinic or clinician is enrolled. **Included** Tennessee Oncology practices will be randomly assigned to usual care or intervention groups. When enrollment starts, clinicians in the intervention clinics will receive the EHR nudge for palliative care referral for each eligible patient and based on the clinician response (opt-out or default), the research coordinator will call and offer palliative care consultation visit to the patient.

For the semi-structured interviews, participants will be initially recruited via internal practice email (See **Exhibit 6**) from the clinical research coordinator. If we don't receive enough interest, we will then recruit by visiting the clinicians in-person in their clinics. In-person recruitment will be done by site investigator and/or clinical research coordinator at Tennessee Oncology.

Approximately 20 eligible clinician participants from the intervention group will be interviewed (1) in-person, (2) virtually, or (3) via telephone. To ensure an adequate number of perspectives on the trial, we will use purposive sampling to sample clinicians who performed at or above vs. below the median response to the intervention. The clinical research coordinator will email and schedule the interviews through outlook. A confirmation email will be sent to the clinician 24 hours before the interview unless the interview will occur less than 24 hours after scheduling. Two pilot interviews will be conducted and used in analysis (pending major edits are not required).

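### The 80% power in section 6.5 makes no visible allowance for randomising practices; it holds only if practices hardly differ, and the SD of 10% is undefined

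*Combined protocol and SAP*

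**What the plan says.** Practices are the unit of randomisation. Section 4.1 says "We will randomize practices into two arms using permuted block randomization to balance practice size, baseline palliative care referral rate", and section 4.9 repeats that "Tennessee Oncology practices will be randomly assigned to usual care or intervention groups". Sections 4.1 and 4.4 put the number at up to 17. Section 4.1 gives the target as about 400 patients and 40 clinicians; section 4.4 has "up to 80 clinicians to assess response to behavioral nudges to refer to palliative care at up to 17 practices within Tennessee Oncology".

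The power statement is in section 6.5. Its inputs are "Assuming baseline palliative care rate=26.9% (SD=10%), a 10% dropout rate, two-sided alpha=0.05", and its conclusion is that "a sample of 360 patients (180 intervention, 180 control) will provide 80% power to detect a meaningful 15 percentage-point increase in palliative care visits". On analysis, the same section says: "The unit of analysis is the patient. We will use multilevel mixed-effects models, adjusted for relevant covariates, to assess outcomes".

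Section 6.5 gives no ICC, design effect, number of practices or practice size. No ICC or design effect appears elsewhere in the document. Nothing says what the SD of 10% measures or how it enters the calculation.

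**The concern.** When practices are randomised, patients of the same practice carry overlapping information, so the effective sample is smaller than the patient count. With only about 17 practices, modest differences between them cost a good deal of power. A calculation that treats 360 patients as independent then overstates the power for the primary endpoint.

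The plan itself treats practice differences as relevant: it balances the allocation on baseline referral rate. If practices do differ in their visit rates, a null result would be read as coming from a trial with 80% power when the power was lower, by an amount that readers cannot work out. Section 4.7 describes the work as leading to an application for a multi-institutional trial, so a misread null would matter.

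**Working it through.** **Inputs.** From section 6.5: control rate 0.269, intervention rate 0.269 + 0.15 = 0.419, two-sided alpha 0.05, 360 patients, 10% dropout, so 324 evaluable (162 per arm). From sections 4.1 and 4.4: up to 17 practices and about 400 patients. 400 less 10% is 360 evaluable, shown as a second case. Equal practice sizes are assumed. All powers are for 15 points.

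**1. Reproducing the 80% with independent patients.** Binomial variances are 0.269 × 0.731 = 0.1966 and 0.419 × 0.581 = 0.2434. The standard error is √[(0.1966 + 0.2434)/162] = 0.0521, and power is Φ(0.15/0.0521 − 1.96) = 82.1%, or 81.4% with a pooled null variance. With 180 per arm it is 85–86%. The stated 80% therefore matches a calculation with no clustering term.

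**2. Reproducing it with the SD of 10%.** A t-test on practice rates with SD 0.10 and difference 0.15 gives 79.7% (8 + 8 practices, 14 df) or 82.2% (9 + 8, 15 df). But with 324/17 = 19.06 patients per practice, binomial error alone gives a practice rate an SD of √(0.1966/19.06) = 10.2 points at 26.9% and √(0.2434/19.06) = 11.3 points at 41.9%. A total SD of 10 points leaves no room for real differences between practices. Adding a true SD of 10 points raises the total to 14.3–15.1 points, and the 9 + 8 power falls to about 50%.

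The 10% cannot be a patient-level SD: for a binary outcome at 26.9% that is √0.1966 = 44%.

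**3. Power with clustering.** Design effect = 1 + (m − 1) × ICC, where m is evaluable patients divided by 17; patients per arm are divided by the design effect. The documents give no ICC, so these values are assumptions. Normal reference, unpooled variance:

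| Assumed ICC | 324 evaluable (m = 19.06) | 360 evaluable (m = 21.18) |
|---|---|---|
| 0 | 82% | 86% |
| 0.01 | 75% | 79% |
| 0.02 | 69% | 73% |
| 0.10 | 40% | 42% |

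The largest ICC that keeps 80% is 0.0031 (unpooled) or 0.0020 (pooled) with 324 evaluable, and 0.0086 or 0.0075 with 360. With a t reference on 17 − 2 = 15 df, power at ICC 0 is already 77% (324) or 81% (360).

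**4. What the SD of 10% could mean.**

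- *True between-practice SD.* ICC = 0.10²/0.1966 = 0.051. With 324 evaluable the design effect is 1 + 18.06 × 0.0509 = 1.92, the effective sample is 324/1.92 = 169, and power is 54–55% (normal) or 49% (15 df). With 360 evaluable the design effect is 2.03 and power is 56–57% or 51%. The difference detectable with 80% power is 20–22 points.
- *SD of observed practice rates.* Part of it is then sampling error: between-practice variance = (0.01 − 0.1966/n)/(1 − 1/n) for n past patients per practice. For assumed n of 20, 30, 50 and 100 the ICC is 0.001, 0.018, 0.031 and 0.041, and power is 81%, 70%, 63% and 59% (324, normal).
- *Between-clinician SD with no practice effect.* For 40 to 80 clinicians, power is 69–76% (324) or 72–80% (360).

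**The case against.** The strongest reply is that what drives power is the practice variation left after design and adjustment. The allocation is balanced on practice size and baseline referral rate, and the model adjusts for covariates. If such factors explained half or three quarters of a true between-practice variance of 0.10² (an assumption), power with 324 evaluable would be about 66% or 74%, and with 360 about 69% or 77%. This stands as a reason not to treat 54–55% as the trial's power. It does not rescue the 80%: the plan quantifies no such gain, does not name the covariates, and balances on referrals whereas the endpoint is completed visits.

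Second, 54–55% applies one ICC to both arms. Holding the SD at 10 points in each arm instead gives 57% (51% with 15 df) with 324 evaluable and 59% (54%) with 360, about 2 points higher. That is fair and changes nothing of substance.

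Third, at 360 evaluable and an ICC of 0.01 the power is 79%, essentially the stated figure. That is also true, but section 6.5 makes its claim for 360 patients with 10% dropout.

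Fourth, the planned analysis is multilevel, so the omission does not in itself bias the estimate or the test. Agreed; but a model that allows for clustering does not supply power that the calculation left out.

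**Conclusion.** The concern holds. Both routes that reproduce 80% require practices with almost no real difference in visit rates: an ICC of at most 0.002–0.003 with 324 evaluable patients, or 0.008–0.009 with 360. The plan neither states nor justifies this.

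The size of the shortfall cannot be fixed from the documents, because every ICC used here is assumed and the SD of 10% has several readings. Across those readings and the assumed ICCs, power with 324 evaluable runs from about 40% to about 81%. These figures assume 17 equal practices (apart from the clinician reading); unequal sizes or fewer practices would lower them, while effective balancing and adjustment would raise them. This should be corrected, since it concerns the power claim for the primary endpoint.

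**What to change.** In section 6.5:

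1. Say what the SD of 10% describes and where it comes from.
2. State an ICC, or a range with its basis, together with the number of practices and their expected sizes.
3. Replace the 80% statement with power or the detectable difference under practice randomisation. Suggested wording: *With [k] practices of about [m] evaluable patients and an ICC of [x], the design effect is [d] and power for a 15-point difference is [p]%; over ICCs from [low] to [high] it is [p1]% to [p2]%.*
4. Name practice as the random intercept in the primary model and pre-specify a small-cluster reference, such as t with about 15 df or a permutation test over the practice allocation. Section 6.5 states neither the level nor the test.
5. List practice size and baseline referral rate, already held for the allocation, among the adjustment covariates.

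The cost is wording, tracing the source of the SD, and probably a less favourable stated power. The small-cluster reference accounts for about 5 points of that (82% to 77% at ICC 0, 55% to 49% at ICC 0.051, 324 evaluable). No extra patients or data are needed.

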6.6 RISKS & BENEFITS

The risk/benefit ratio of this study is very favorable. The study team will take necessary steps to maintain confidentiality and privacy throughout the study period.

The potential risks associated with this study are minimal. Breach of data is a potential risk that will be mitigated by using HIPAA compliant and secure data platforms as described. There are also potential emotional risks to patients if they misunderstand the role of palliative care. Our research coordinator will be trained in helping patients and their caregivers understand the supportive role of palliative care.

There may be some emotional discomfort or distress with doing patient-reported surveys. If this occurs, subjects will have the option to stop the phone call and questionnaire, and we will also provide support resources to help cope with this afterwards including referral to our internal psychology team or state-funded mental health support crisis [contact]).

Potential study benefits include improved consideration of stakeholder input into our planned palliative care intervention and more informed decision-making regarding palliative care treatment plans.

7. DATA COLLECTION AND MANAGEMENT

7.1 DATA QUALITY ASSURANCE

Tennessee Oncology will supply Electronic Medical Record (EMR) specifications for this study. Tennessee Oncology will be responsible for data management of this study, including quality checking of the data. Data entered manually will be collected via EMR using source documents. Clinics will be responsible for data entry into the EMR system. In the event of discrepant data, Tennessee Oncology will request data clarification from the clinics to resolve electronically in the Electronic Data Capture (EDC) system.

Tennessee Oncology will produce a Data Quality Plan that describes the quality checking to be performed on the data. EMR and correction documentation will be maintained in the EDC system's audit trail. System backups for data stored at the clinic(s) and records retention for the study data will be consistent with the Tennessee Oncology standard procedures.

Tennessee Oncology will perform oversight of the data management of this study, including approval of data management plans and specifications. Tennessee Oncology standard procedures will be used to handle and process the electronic transfer of these data.

